3.1. Protocol Deviations

Important protocol deviations (including deviations related to study inclusion/exclusion criteria, conduct of the trial, patient management or patient assessment) will be summarised and listed.

Protocol deviations will be tracked by the study team throughout the conduct of the study in accordance with the Protocol Deviation Management Plan.

- Data will be reviewed prior to freezing the database to ensure all important deviations and deviations which may lead to exclusion from the analysis are captured and categorised on the protocol deviations dataset.
- This dataset will be the basis for the summaries and listings of protocol deviations.

A separate listing of all inclusion/exclusion criteria deviations will also be provided. This summary will be based on data as recorded on the inclusion/exclusion page of the eCRF.

Prospective approval of protocol deviations to recruitment and enrolment criteria, also known as protocol waivers or exemptions, is not permitted.

4. CONSIDERATIONS FOR DATA ANALYSES AND DATA HANDLING CONVENTIONS

Table 2 provides an overview of appendices within the RAP for outlining general considerations for data analyses and data handling conventions.

Table 2 Overview of Appendices

Section	Component
10.1	Appendix 1: Time & Events
10.2	Appendix 2: Assessment Windows
10.3	Appendix 3: Study Phases and Treatment Emergent Adverse Events
10.4	Appendix 4: Data Display Standards & Handling Conventions
10.5	Appendix 5: Derived and Transformed Data
10.6	Appendix 6: Reporting Standards for Missing Data
10.7	Appendix 7: Abbreviations & Trade Marks
10.8	Appendix 8: List of Data Displays
10.9	Appendix 9: Example Mock Shells for Data Displays

4.1. General Considerations

• This is a longitudinal, prospective study of healthy participants and participants who have sustained thermal injury.

Unless otherwise stated, the following rules will apply:

- Summaries and displays will be presented by study group and visit (without the group information in visit).
- The following statistics will be used to summarise the data, unless otherwise specified:
 - o Continuous Variables: number of observations (n), mean, standard deviation (SD), standard error (SE), median, minimum and maximum.
 - Categorical Variables: number of observations (n), frequency counts and percentages.
- Summaries by Visit: Only scheduled visits will be presented, unless otherwise stated. Unscheduled visits will be listed but will not contribute towards any summary statistics/analyses, unless otherwise stated.
- Summaries by study group: Study group (Healthy Participants and TI Participants) will be used instead of treatment group in all the tables and listing.
- No imputation will be done for missing values across visits, individual missing scores will be considered missing.

4.2. Baseline Definitions

For efficacy and biomarker endpoints, the baseline value will be Day 1 for both the groups. In case of missing Day 1 assessment, baseline would be set to missing.

Parameter	 	Study Assessments Considered as Baseline							
	Screening [1]	Day 1 (Baseline)							
Efficacy Assessments									
L/M Ratio		X	Day 1 (Baseline)						
Fractional excretion of sucralose		X	Day 1 (Baseline)						
Biomarkers Assessments									
Markers of intestinal mucosal damage		X	Day 1 (Baseline)						
Bacterial markers of translocation		X	Day 1 (Baseline)						
Safety Assessments									
Vital Signs	Χ		Screening						
Laboratory Assessments									
Haematology	Χ		Screening						
Clinical Chemistry	Х		Screening						
Routine Urinalysis	Χ		Screening						
[1] Screening = 1-2 Wks Prior to Day 1 (Heal	[1] Screening = 1-2 Wks Prior to Day 1 (Healthy Participants).								

4.2.1. Derivations and Handling of Missing Baseline Data

For untransformed data, change from baseline at each time point is expressed as a difference (value at time point – value at baseline).

Definition	Reporting Details					
Change from Baseline [1]	= Post-Baseline Visit Value – Baseline Value					
% Change from Baseline [1]	= 100 x [(Post-Baseline Visit Value – Baseline Value) / Baseline Value]					
[1] If the baseline value is missing the change from baseline derivations will also be missing						

5. STUDY POPULATION ANALYSES

5.1. Overview of Planned Study Population Analyses

• The Study Population analyses will be based on the Screened, Evaluable or Safety population, as appropriate unless otherwise specified.

Study population analyses including analyses of subject's disposition, protocol deviations, demographic and baseline characteristics, prior and concomitant medications, and exposure and treatment compliance will be based on GSK Core Data Standards. Details of the planned displays are presented in Appendix 8: List of Data Displays.

6. EFFICACY ANALYSES

6.1. Primary Analyses

6.1.1. Endpoint / Variables

• Lactulose/mannitol ratio

6.1.2. Summary Measure

The administration of the STM is for the purpose of intestinal permeability measurement and is not therapeutic, therefore no efficacy will be assessed.

Absolute, change and % change in lactulose/mannitol ratio values will be used for analysis.

6.1.3. Population of Interest

The primary analyses will be based on the evaluable population, unless otherwise specified.

6.1.4. Statistical Analyses / Methods

Endpoints defined in Section 6.1.1 will be summarised by study group, timepoint and visit. Data will summarise mean, standard deviation, standard error, minimum, median, maximum and N.

No formal statistical analysis will be performed.

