10.6. Analyses of lactulose/mannitol ratio

In all analyses the variable TBSA will be a categorical variable defined as “Yes” for thermally injured participants, and “No” for healthy participants.

Differences in permeability at entry

Intestinal permeability biomarkers will be summarised by TBSA group and overall. Data will summarised by geometric mean, CV, minimum, maximum and N. A model will be fitted, defined as

$\text{Log (L/M ratio)} = \text{intercept} + \text{TBSA}$

Trajectory of the L/M ratio over time

Intestinal permeability biomarkers will be summarised over time, by TBSA group and overall. Data will summarise geometric mean, CV, minimum, maximum and N. A model will be fitted, defined as

$\text{Log (L/M ratio at time X / L/M ratio at entry)} = \text{intercept} + \text{Time} + \text{TBSA} + \text{Time} * \text{TBSA}$.

This will be a repeated measurement analysis and will assess the rate of improvement in L/M ratio over time, and assess how this changes relative to healthy participants. If required, further modelling assessing more complex relationships between L/M ratio and time may be undertaken. Given this is an exploratory study the most appropriate variance-covariance matrix regarding the correlation of data over time will be explored as part of the statistical analysis.

Data from this model may also be used to estimate the time to 50% improvement (or other degrees of improvement) in L/M ratio in relation to L/M ratio values seen in healthy participants. This will be used to assess the clinical relevance and sensitivity of such measures.

A model fitting $\text{log (AUC of L/M ratio)} = \text{intercept} + \text{TBSA}$ will also be fitted. AUC will be calculated using all measurements taken over time. This will provide a summary of the weighted average L/M ratio value over time.

The use of %TBSA will also be assessed in the above analyses as a continuous covariate. The effects of age and Baux score will also be evaluated to understand differences in intestinal permeability in these groups [Osler, 2010].

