10.5. Appendix 5: Derived and Transformed Data

10.5.1. General

Multiple Measurements at One Analysis Time Point

- Mean of the measurements will be calculated and used in any derivation of summary statistics but if listed, all data will be presented.
- If there are two values within a time window the value closest to the target day for that window will be used. If values are the same distance from the target, then the mean will be taken.

Study Day

- Calculated as the number of days from First STM Dose Date:
 - Ref Date = Missing → Study Day = Missing
 - Ref Date < First STM Dose Date → Study Day = Ref Date First STM Dose Date
 - Ref Data ≥ First STM Dose Date → Study Day = Ref Date (First STM Dose Date) + 1

Age

Age = Screening date – Date of Birth
 Date of birth will be imputed based on the assumption that all subjects were born on the 30th June (30 Jun YYYY).

Baux score

Baux score: Age + % Total Body Surface Area (TBSA) burned

10.5.2. **Efficacy**

Fractional Excretion of Lactulose/Mannitol/Sucralose

Data is provided to S&P in the form of quantity of material in micrograms/litre, based on a sample of urine.

Fractional excretion (FE) of lactulose or mannitol or sucralose = (urine concentration (micrograms/litre) × total urine volume excreted in litre) / probe input (micrograms).

Where,

- Urine concentration is provided in the BIOMARKER dataset,
- Urine volumes excreted are provided in the BIOLINK dataset,
- Probe input refers to the total STM taken (as per Table 7.1 of the protocol-5g Lactulose, 2g Mannitol and 2g Sucralose)

Urine concentration in the BIOMARKER dataset will be provided at two timepoints per visit (0-5hr) and (0-24hr)

FE will be calculated for timepoints 0-5 and 0-24 hours for Lactulose, Mannitol and Sucralose.

For calculations of the 0-24 FE's, total urine volume will be based on the following:

Total urine=urine excreted 0-5 hrs + urine excreted 5-24 hours.

Note: If urine excreted 0-5 hrs is missing then total urine should be considered missing.

Note: 1g=1000000 micrograms

L/M ratio

L/M ratio = FE lactulose / FE mannitol

Healthy Participant – Average

• Average = Mean of all data available at all timepoint for each healthy participant.

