10.8.6. Efficacy Figures

Efficacy	Efficacy: Figures						
No.	Population	IDSL / Example Shell	Title	Programming Notes	Deliverable [Priority]		
L/M ratio	L/M ratio						
2.1.	Evaluable	EFF_F1	Individual Plot of Absolute L/M Ratio Values Over Time for Healthy Subjects.	Y-axis: Absolute Values Plot by Timepoint	SAC		
2.2.	Evaluable	EFF_F2	Individual Plot of Absolute L/M Ratio Values Over Time for TI Subjects.	Y-axis: Absolute Values Plot by Timepoint Average value of Healthy Subjects will be used as reference line.	SAC		
2.3.	Evaluable	EFF_F2	Individual Plot of %Change L/M Ratio Values Over Time for TI Subjects.	Y-axis: %CFB Values Plot by Timepoint Average value of Healthy subjects will be used as reference.	SAC		
Fraction	al excretion of s	ucralose					
2.4.	Evaluable	EFF_F1	Individual Plot of Absolute Sucralose Values Over Time for Healthy Subjects.	Y axis: Absolute Values Plot by Timepoint	SAC		
2.5.	Evaluable	EFF_F2	Individual Plot of Absolute Sucralose Values Over Time for TI Subjects.	Y axis: Absolute Values, Plot by Timepoint Average value of Healthy subjects will be used as reference.	SAC		
2.6.	Evaluable	EFF_F2	Individual Plot of %Change Sucralose Values Over Time for TI Subjects.	Y axis: %CFB Values Plot by Timepoint Average value of Healthy subjects will be used as reference.	SAC		

L/M ratio	L/M ratio and Fractional excretion of sucralose					
2.7.	Evaluable	EFF_F3	Individual Plot of Absolue L/M ratio and Sucralose Values Over Time for TI Subjects.	Y axis: Absolute Values Plot by Timepoint Average values of Healthy subjects will be used as reference.	SAC	
2.8.	Evaluable	EFF_F3	Individual Plot of %Change L/M ratio and Sucralose Values Over Time for TI Subjects.	Y axis: %CFB Values Plot by Timepoint Average values of Healthy subjects will be used as reference.	SAC	

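### The SAP replaces the protocol's geometric mean and CV for the L/M ratio with mean, SD and SE, drops the pooled summary, and lists neither change in its table of departures

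*SAP*

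**What the plan says.** Protocol 10.6 (Amendment 2, the version the SAP cites) attaches no condition to its L/M summaries. At entry: "Data will summarised by geometric mean, CV, minimum, maximum and N". Over time: "Data will summarise geometric mean, CV, minimum, maximum and N". Both are to be given for each group and for the two groups together. The same section models log L/M, and the power illustration in protocol 10.2 uses a log-scale SD of 1.15.

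SAP 6.1.4 says of L/M: "Data will summarise mean, standard deviation, standard error, minimum, median, maximum and N". SAP 4.1 gives the same set for continuous variables in general. Shell EFF_T1 prints it for healthy and thermally injured (TI) participants, with no pooled row. On the scale of change, SAP 6.1.2 says "Absolute, change and % change in lactulose/mannitol ratio values will be used for analysis", and SAP 4.2.1 defines % change as "100 x [(Post-Baseline Visit Value – Baseline Value) / Baseline Value", closing the bracket there.

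For the healthy reference, SAP 10.5.2 gives a per-participant value: "Average = Mean of all data available at all timepoint for each healthy participant". The group line comes from the note to shell EFF_F1, which averages over all the healthy data. Figure 2.2 carries that line onto the TI plots: "Average value of Healthy Subjects will be used as reference line".

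SAP 1.1 presents Table 1 as the list of changes from the protocol analysis. Its row for co-primary objective 1 says that L/M at entry will be summarised without a formal comparison, because of the limited sample. No row mentions geometric mean, CV, scale or the pooled summary, and there is no row for co-primary objective 2.

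**The concern.** With the models dropped, descriptive tables and plots are the whole of the co-primary output, so the choice of statistic matters more than it would beside a model. Three TI participants are a good reason not to fit a model. They do not explain a move from the log scale to the raw scale, and a reader comparing the report with the protocol would find no account of it.

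On skewed ratio data the raw scale has two effects. A plain-mean healthy line sits above the centre of the healthy values, so a TI value plotted against it looks less raised than it is. Mean % change also leans upward when nothing has changed, because a doubling counts as +100% and a halving as only -50%. Healthy participants are measured on Days 1, 8 and 15 as a stable reference, so their % change rows would tend to show a rise.

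**Working it through.** **The plan's own figure.** Inputs from protocol 10.2: 25 TI and 15 healthy participants, a 3-fold ratio (ln 3 = 1.0986), log SD 1.15, two-sided 0.10. The standard error is 1.15 × √(1/15 + 1/25) = 0.3756, and 1.0986/0.3756 = 2.925. The normal approximation gives power 0.900. The two-sample t with 38 degrees of freedom gives 0.890, matching the stated 89%. The protocol therefore planned L/M on the log scale.

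**Healthy reference line.** Assume log-normal L/M with healthy log SD h. Expected arithmetic mean divided by geometric centre is exp(h²/2). The typical value is the median of simulated lines for the planned 15 healthy participants (the SAP text does not give the actual number): 200,000 runs with one value each, and 100,000 runs with three visits each and half the log variance between participants.

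| h | Expected | Typical, 1 value each | Typical, 3 visits each |
|---|---|---|---|
| 0.3 (assumed) | 1.05 | 1.04 | 1.04 |
| 0.5 (assumed) | 1.13 | 1.12 | 1.13 |
| 0.8 (assumed) | 1.38 | 1.33 | 1.35 |
| 1.15 (protocol 10.2) | 1.94 | 1.77 | 1.83 |

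The geometric mean of the same simulated data centres on 1.00.

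**Mean % change with no true change.** Assume independent within-subject log deviations with SD w on Day 1 and at the later visit. The log ratio then has mean 0 and variance 2w², so expected % change is 100 × (exp(w²) − 1). Typical values and the share of positive samples come from 200,000 simulated samples.

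| w (assumed) | Expected | Typical, n=3 (share positive) | Typical, n=15 (share positive) |
|---|---|---|---|
| 0.3 | +9% | +6% (59%) | +9% (77%) |
| 0.5 | +28% | +16% (64%) | +25% (87%) |
| 0.8 | +90% | +41% (69%) | +74% (94%) |

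The geometric mean ratio is above 1 in half of such samples, and the median % change centres on zero.

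**What the log scale cannot do.** At n=3 and log SD 1.15, the 95% sampling range of a geometric mean is exp(±1.96 × 1.15/√3), or 0.27 to 3.67 times the truth. The change of statistic removes a systematic lean; it gives little precision for the TI group.

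**A separate conflict.** For the % change plots (Figures 2.3 and 2.8 for L/M), SAP Appendix 8 sets the reference at the healthy average. The notes to shells EFF_F2 and EFF_F3 in Appendix 9 allow either zero or the healthy mean % change, with the choice left until the data are seen. By the second table, those two lines could differ noticeably.

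**The case against.** The strongest case against is that this is a documentation point with little consequence. SAP 6.1.4 adds the median, which under log-normality centres on the same value as the geometric mean. Individual values are plotted and appear in Listing 24, so geometric statistics can be recovered. No test is planned, protocol 10.1 calls the analysis exploratory, and SAP Table 1 says that development of the molecule has ended. SAP 6.1.4 also states openly that there is no formal analysis, so the loss of the models is disclosed in the body even where Table 1 is silent. Protocol section 10 allows deviations to be described in an addendum and justified in the study report, and neither is available here. All of this stands, and it limits the weight of the point.

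Two textual defences are weaker. Protocol 10.3 makes geometric mean and CV conditional on log-normality, but 10.6 is specific to these measures and sets no condition. The SAP writes mean, not arithmetic mean, so the arithmetic reading is an inference. It is a strong one: the mean is paired with SD and SE, change is a raw difference, and no derivation takes logs.

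Three stronger readings should be resisted:
- A reader might infer that the protocol requires a geometric reference line, a log axis or a ratio to Day 1. It does not. The log ratio to entry in 10.6 is a model response, and 10.6 names no reference line.
- A reader might apply the factor of 1.94 to the healthy line. The SD of 1.15 was used for the comparison as a whole and may not describe healthy participants.
- A reader might infer that a finding on return to normal is distorted. SAP 1.3 says nobody reached Day 28, so that question is not assessed.

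**Conclusion.** The point holds and is minor. Two explicit summary requirements of protocol 10.6, geometric mean with CV and the pooled summary, are missing from the SAP, and Table 1 records neither. Table 1 also omits co-primary objective 2. The small sample explains dropping the models but not the change of scale.

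The direction of the effect rests on L/M being roughly log-normal, which the protocol's own modelling implies but the documents do not demonstrate. The sizes rest on assumed SDs: an expected healthy line 1.05 to 1.38 times the healthy centre, and an expected mean % change of +9% to +90% with no true change. No healthy or within-subject SD is given in the documents. The textual departure depends on none of these assumptions.

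**What to change.** 1. In Tables 2.1 to 2.3, keep the planned statistics, add geometric mean and geometric CV, and show change as the geometric mean ratio to Day 1.
2. State one convention for zero or non-detect sugar values so that logs can be taken. It may seldom be needed, since protocol 5.4.5 chose the doses with urinary detection in mind. The non-detect rule in SAP 10.5.3 is written for safety laboratory parameters.
3. As an improvement beyond the protocol text, draw the healthy L/M reference as a geometric mean on a log axis.
4. EFF_T1 also serves sucralose (Tables 2.4 to 2.6), and protocol 10.6 speaks of permeability biomarkers generally. Apply the same statistics there, or split the shell.
5. Add Table 1 rows, with reasons, for any departure that is kept: summary scale, pooled summary, and co-primary objective 2.
6. Separately, reconcile Appendices 8 and 9 on the % change reference line before the data are reviewed.

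The cost is edits to EFF_T1 and the L/M figure shells, one line on zeros, and a few table rows. No new data are needed, and the planned sample size and power are unaffected.

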6.2. Exploratory Analyses

6.2.1. Endpoint / Variables

• Fractional excretion of sucralose

6.2.2. Summary Measure

Absolute, Change and %Change in the fractional excretion of sucralose over

time.

6.2.3. Population of Interest

The exploratory efficacy analyses will be based on the evaluable population, unless otherwise specified.

6.2.3.1. Statistical Analyses / Methods

Details of the planned displays are provided in Appendix 9: List of Data Displays and will be based on GSK data standards and statistical principles.

Unless otherwise specified, endpoints defined in Section 6.2.1 will be summarised using descriptive statistics and listed.

6.2.3.2. Statistical Methodology Specification

There will be no planned statistical analysis.

7. SAFETY ANALYSES

The safety analyses will be based on the "Safety" population, unless otherwise specified.

7.1. Adverse Events Analyses

Adverse events analyses including the analysis of adverse events (AEs), Serious (SAEs) and other significant AEs will be based on GSK Core Data Standards. The details of the planned displays are provided in Appendix 8: List of Data Displays.

NOTE: As detailed in Section 9.2.1 of the protocol, only AEs deemed to be related to procedures or requirements unique to the HESTIA study will be recorded/reported for thermally injured participants. All other AEs will be recorded/reported through the SIFTI-2 study.

Also, as given in Section 12.4 (Events NOT Meeting the AE Definition) in protocol, any clinically significant abnormal laboratory findings or other abnormal safety assessments which are associated with the underlying disease, unless judged by the investigator to be more severe than expected for the participant's condition will be considered as disease related event. Table 3 in protocol provides a list of commonly occurring AEs in participants with severe thermal injury which may meet this definition and will be entered as disease related events.

7.2. Clinical Laboratory Analyses

Laboratory evaluations including the analyses of Chemistry laboratory tests, Hematology laboratory tests and Urinalysis will be based on GSK Core Data Standards. The details of the planned displays are in Appendix 8: List of Data Displays.

Table 3 Protocol-Required Safety Laboratory Assessments for Healthy Participants:

Laboratory Assessments	Parameters											
	Platelet Count		WBC count with Differential:									
Hematology	RBC Count		Neutrophils Lymphocytes									
riomatology	Hemoglobin		Monocytes Eosinophils									
	Hematocrit			Basophils								
	Urea	Potassium			Total bilirubin							
Clinical Chemistry	Creatinine	Sodium	Alanine Amin (ALT)	otransferase	Total Protein							
,	Glucose non- fasting	Calcium	phatase									
Routine Urinalysis	pH, glucose, protein, blood, ketones by dipstick Microscopic examination (if blood or protein is abnormal)											

7.3. Other Safety Analyses

The analyses of non-laboratory safety test results including vital signs will be based on GSK Core Data Standards, unless otherwise specified. The details of the planned displays are presented in Appendix 8: List of Data Displays.

8. BIOMARKER ANALYSES

8.1. Exploratory Biomarker Analyses

8.1.1. Endpoint / Variables

As this is an exploratory study, a number of data presentations will be produced for a set of biomarkers to understand how they change over time. In order to simplify the investigation, the biomarkers will be grouped into biomarkers of intestinal damage and bactorial markers of translocation. All endpoints will be summarised by mean, standard deviation, standard error, median, minimum, maximum and number of subjects, by study group. These groupings of biomarkers are provided in Table 4.

Table 4 List of biomarkers considered for final analysis

Biomarker Grouping	Parameters
Markers of intestinal mucosal damage	iFABP, citrulline, Zonulin-1, Occludin
Bacterial markers of translocation	sCD14, Microbial Metabolites: (Glycodeoxycholic acid, Taurodeoxycholic acid, Taurodeoxycholic acid, Taurolithocholic acid, Oxocholic acid, Ursodeoxycholic acid)

